**2****PROTOCOL SYNOPSIS**

**Title** A Phase 4, Open-label Treatment, Randomized, Multicenter, 2-arm, Parallel-group, Pilot Study of Adherence to Lumacaftor/Ivacaftor in CF Subjects Homozygous for the *F508del-CFTR* Mutation

**Brief Title** A Pilot Study to Evaluate the Use of Smart Adherence Technology to Measure Lumacaftor/Ivacaftor Adherence in CF Subjects Homozygous for the *F508del-CFTR* Mutation

**Clinical Phase and Clinical Study Type** Phase 4, Adherence

**Objectives** Primary

To evaluate the impact of smart adherence technology for monitoring LUM/IVA adherence rates among subjects 16 years of age and older with CF who are homozygous for the *F508del-CFTR* mutation

Secondary

To collect subject and physician feedback on the use of smart adherence technology to monitor LUM/IVA adherence

**Endpoints** Primary Endpoint

Mean percentage adherence to LUM/IVA treatment over 48 weeks

Secondary Endpoints

- Mean percentage adherence to LUM/IVA treatment over 24 weeks
- Mean percentage adherence to LUM/IVA treatment from Week 25 through Week 48
- Proportion of subjects with  $\geq 80\%$  LUM/IVA adherence over 24 weeks
- Proportion of subjects with  $\geq 80\%$  LUM/IVA adherence over 48 weeks
- Proportion of subjects with  $\geq 80\%$  LUM/IVA adherence from Week 25 through Week 48
- Proportion of subjects with a non-physician-directed LUM/IVA interruption  $\geq 72$  hours over 48 weeks
- Number of non-physician-directed LUM/IVA interruptions  $\geq 72$  hours over 48 weeks
- Time to the first non-physician-directed LUM/IVA interruption  $\geq 72$  hours over 48 weeks

[REDACTED]

[REDACTED]

[REDACTED]

[REDACTED]

[REDACTED]

Number of Subjects	Approximately 75 subjects will be enrolled.
Study Population	Male and female subjects 16 years of age and older with CF who are homozygous for the F508del-CFTR mutation
Investigational Drug	
Active substance: LUM and IVA (fixed-dose combination [FDC] with LUM and IVA)
 
Activity: CFTR corrector and potentiator (chloride ion secretion)
 
Strength and Route of Administration: 200-mg LUM/125-mg IVA (200/125 mg) film-coated tablets for oral administration
 
Dose Regimen: LUM 400 mg/IVA 250 mg every 12 hours (q12h)

Smart Adherence Technology	

Smart Pill Bottle, activated

Smart Pill Bottle (control), de-activated alerts and feedback features

Study Duration	The total duration is approximately 56 weeks (up to 28 days for the Screening Period, 48 weeks for the Treatment Period, and 28 days ( $\pm$ 7 days) for Safety Follow-up Period, if applicable)
Study Design	
This is a Phase 4, open-label, randomized, multicenter, 2-arm, parallel-group pilot study evaluating LUM/IVA adherence. Each study arm will include a smart technology with either active or inactive dosing alert features.
 
This study includes:
 

Screening Period (Day -28 through Day -1)

Treatment Period (Day 1 through Week 48)

Safety Follow-up Visit at Week 52 (28 [<math>\pm</math> 7] days after the final dose of LUM/IVA)

 
Approximately 75 subjects will be enrolled in this study. All subjects will receive LUM 400 mg/IVA 250 mg q12h through Week 48.
 
Subjects will be stratified by age (<23 versus <math>\geq</math>23 years of age) and forced expiratory volume in 1 second (FEV1) severity (<70% versus <math>\geq</math>70% predicted) determined at the Screening Period and then randomized (2:1) to 1 of the following 2 smart adherence technology study arms:
 

Study Arm A: Smart Pill Bottle, activated

Study Arm B: Smart Pill Bottle (control), de-activated alerts and feedback features

 
Subjects will receive standardized education on the benefit of LUM/IVA, LUM/IVA adherence, and training on the use of the assigned smart adherence technology. During applicable study visits, subjects will complete adherence and technology satisfaction assessments. Physicians will also complete a technology satisfaction questionnaire adherence assessments.

**Assessments** **Adherence:** Smart Adherence Technology-Reported Adherence

[REDACTED]

[REDACTED]

[REDACTED]

[REDACTED]

**Safety:** Adverse events, ophthalmologic examinations, clinical laboratory assessments, vital signs, physical examinations

[REDACTED]

**Statistical Analyses** Statistical analysis details will be provided in the Statistical Analysis Plan (SAP).

The primary endpoint is the mean percentage adherence to LUM/IVA treatment over 48 weeks. Assuming a standard deviation (SD) of 8, a sample size of 50 subjects in Study Arm A and 25 in Study Arm B will have 80% power to detect a treatment difference of 5.6% between the means of the 2 arms using a 2-sided, 2-sample t-test at the 0.05 significance level.

The primary analysis for the primary endpoint variable will be based on an analysis of covariance (ANCOVA) with mean percentage adherence over 48 weeks as the dependent variable, Study arm as a fixed effect with covariates for age (<23 versus  $\geq 23$  years old), FEV1 (<70% versus  $\geq 70\%$  predicted), [REDACTED], and sex (male versus female), at Screening. [REDACTED]

[REDACTED]

[REDACTED]

[REDACTED]

Summary statistics for each study arm will be provided. Primary and secondary analyses of adherence will be performed through smart technology generated data. A complementary analysis based on pill count and missing/interruption of dose will also be conducted. Summary of weekly adherence data will be provided; pattern of adherence over 48 weeks will be plotted and may be modeled using mixed effects models.

No interim analysis is planned for this study.

### 3 SCHEDULE OF ASSESSMENTS

Schedules of Assessments are shown in Table 3-1 (Screening Period) and [Table 3-2](#) (Treatment Period and Safety Follow-up Visit).

All visits are to be scheduled relative to the Day 1 Visit.

**Table 3-1 Screening Period Assessments – Study VX15-809-114**

Assessment	Screening Period Day -28 to Day -1
Informed consent and assent (where applicable)	X
Inclusion and exclusion criteria review	X
Demographics	X
Height, weight, and BMI	X
Review of medical history (includes CFTR genotype) a	X
Ophthalmologic examination b	X
Prior and concomitant medications	X
Vital signs c	X
Physical examination d	X
Spirometry e	X
Serum pregnancy test (all female subjects of childbearing potential) f	X
Serum FSH g	X
Hematology h	X
Liver Function Testing i	X
AEs and SAEs	Continuous from signing of ICF or assent (where applicable) through Safety Follow-up Visit

AE: adverse event; BMI: body mass index; CF: cystic fibrosis; *CFTR*: *CF transmembrane conductance regulator* gene; FSH: follicle-stimulating hormone; ICF: informed consent form; IVA: ivacaftor; LUM: lumacaftor; PE: physical examination; SAE: serious adverse event; [REDACTED]

a Genotype testing will be performed if this is not documented in medical history. CF genotyping can be waived with documented *CFTR* genotype ([Section 11.5.2](#)).

b An ophthalmologic examination will be conducted by either a licensed ophthalmologist or an optometrist for all subjects <18 years of age. The exam may be waived if there is documentation of an exam within 3 months of the date of informed consent (or assent, when applicable). Subjects with documentation of bilateral lens removal do not need the ophthalmologic examination ([Section 11.5.6](#)).

c Vital signs will be assessed following a 5-minute rest in the seated or supine position.

d Physical examination of all body systems ([Section 11.5.4](#)).

e Spirometry may be performed pre- or postbronchodilator ([Section 11.5.5](#)).

f Any female subject initiating LUM/IVA combination therapy who is considered to be of childbearing potential should have a serum pregnancy test. Women of childbearing potential are defined as: female subjects after puberty unless they are postmenopausal for at least 1 year and have documented FSH levels within the postmenopausal reference range of the performing laboratory, or are surgically sterile.

g Serum FSH levels will be measured for any suspected postmenopausal female subjects with at least 12 months of continuous spontaneous amenorrhea.

h Blood samples will be collected for clinical laboratory assessments ([Section 11.5.2](#)).

i Liver function testing (alanine aminotransferase [ALT], aspartate aminotransferase [AST], gamma-glutamyl transpeptidase [GGT], alkaline phosphatase [ALP], and total bilirubin) must be performed at the scheduled visits ([Section 11.5.2](#)).

**Table 3-2 Treatment Period and Safety Follow-up Visit Assessments – Study VX15-809-114**

Event/Assessment	Day 1	Week 12	Week 24	Week 36	Week 48	Safety Follow-up Week 52 a
Clinic visit	X	X	X	X	X	X
Vital signs b	X	X	X	X	X	X
Physical examination c					X	X d
Liver Function Testing e	X	X	X	X	X	X
Urine pregnancy test (all female subjects of childbearing potential)	X	X	X	X	X	X
Randomization f	X					
Standardized education on adherence	X					
Concomitant medications, treatments, and procedures	X	X	X	X	X	X
Smart Adherence Technology-Reported Adherence g		X	X	X	X	

LUM/IVA drug count i		X	X	X	X	
Ophthalmologic examination j					X	
AEs and SAEs	Continuous from signing of ICF or assent (where applicable)					
LUM/IVA resupply	Every 3 months throughout study					

AE: adverse event; ICF: informed consent form; IVA: ivacaftor; IWRS: interactive web response system; LUM: lumacaftor; PE: physical examination; SAE: serious adverse event; [REDACTED]

a The Safety Follow-up Visit is 28 ( $\pm$  7) days after the last dose of LUM/IVA (Section 8.1.3).

b Vital signs will be assessed following a 5-minute rest in the seated or supine position.

c Symptom-targeted PEs will occur at any time during the study if triggered by AEs or if deemed necessary by the investigator.

d Required for subjects who do not begin commercial LUM/IVA after Week 48 only.

e Day 1 only blood draws will be collected before the first dose of LUM/IVA. Liver function testing (alanine aminotransferase [ALT], aspartate aminotransferase [AST], gamma-glutamyl transpeptidase [GGT], alkaline phosphatase [ALP], and total bilirubin) must be performed at the scheduled visits (Section 11.5.2).

f Randomization must occur after all inclusion and exclusion criteria are met and before the first dose of LUM/IVA. Randomization will be done through IWRS.

g Data will be collected for all subjects throughout the study in real-time. Subjects in Study Arm A will review data with physicians at study visits.

i LUM/IVA drug count will be collected at the end of specified study visits.

j See Section 11.5.6.

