**Table 8-1 Study VX15-809-114 Smart Adherence Technology Study Arms**

Smart Adherence Technology	Activated Features	Access to LUM/IVA Compliance Status	Number (n)
Smart Pill Bottle (Study Arm A)	Real-time dosing data transfer, electronic medication reminders/missed dose alerts (audio, visuals, texts, emails, phone calls)	Site staff and physicians, CRO, Vertex	50
Smart Pill Bottle, Control (Study Arm B)	Real-time dosing data transfer to CRO/Vertex only	CRO/Vertex only	25

CRO: contract research organization

The use of active smart adherence technologies (smart pill bottles) will provide subjects with objective and real-time feedback on dosing adherence, including reminders of upcoming or missed doses. Study physicians will access dosing adherence data and review them with subjects in Study Arm A at scheduled study visits. Subjects in Study Arm B will not receive any alerts, reminders, or real-time feedback on dosing adherence. Study Arm B will provide objective data on dosing adherence without influencing subjects to take a scheduled dose of LUM/IVA.

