## **11.3 Adherence**

### **11.3.1 Smart Adherence Technology-Reported Adherence**

LUM/IVA adherence monitoring will occur throughout the Treatment Period using smart adherence technology. This technology will allow for collection of real-time LUM/IVA compliance by reporting LUM/IVA dosing times each time the smart pill bottles are opened. Only subjects in Study Arm A will review data with study physicians at the study visits listed in [Table 3-2](#).

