#### **12.3.2.4    Study Drug Exposure and Compliance**

Exposure to LUM/IVA (i.e., duration of treatment in days) will be summarized for the FAS in terms of duration of treatment a subject received (in days), defined as the last day minus the first day of LUM/IVA plus 1. Exposure will be summarized by study arms for the FAS.

Primary and secondary analyses of adherence will be performed through smart technology generated data. A complementary analysis based on pill count and missing/interruption of dose

will be conducted. Information on number of pills and drug interruption will be collected from dispensing pharmacy and subjects.

These pharmacy and subject reported compliance data will be summarized for the FAS and will be derived in at least 1 of 2 methods pending data availability:

(1) based on pill counts calculated as:

$$100 \times (\text{total number of tablets taken}) / (4 \times \text{duration of LUM/IVA exposure in days})$$

And/or:

(2) based on medication interruption days using the formula:

$$100 \times [1 - (\text{total number of days LUM/IVA interrupted} \geq 72) / (\text{duration of LUM/IVA exposure})]$$

Duration of treatment and dosing compliance will be summarized by means of descriptive summary statistics.

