8.3.2 Analysis of Adherence Endpoints

Mean percentage adherence to LUM/IVA treatment over treatment duration for all subjects

The percentage adherence over treatment duration for each subject is defined as:

$$100 \times (\text{total number of smart bottle openings over the eligible treatment duration excluding the physician-directed interruption periods of the eligible treatment duration}) / [2 \times (\text{eligible duration of treatment} - \text{the number of physician-directed interruption days of the eligible treatment duration})]$$

Note: (1) the physician-directed interruption is defined as the reported interruptions due to reasons not being “Non-compliance”; (2) if there are more than 2 smart bottle openings at any day, they will be counted as 2 in calculation of the adherence endpoints. (3) the eligible treatment duration = eligible date of last dose – date of first dose + 1, where the eligible date of last dose is defined to be either the CRF collected date of last dose or the last activity date of smart bottle data, whichever is earlier.

Descriptive statistics will be provided by the number of subjects (n), mean, SD, SE, median, min, and max by treatment arm based on FAS. [REDACTED]

The percentage adherence will also be listed.

Mean percentage adherence to LUM/IVA treatment over 0 through 12 weeks for subjects who have at least 12 weeks of eligible smart pill bottle data

Subjects who have at least 12 weeks of eligible smart pill bottle data are defined as those who have at least 12 weeks of eligible treatment duration = eligible date of last dose – date of first dose + 1, where the eligible date of last dose is defined to be either the CRF collected date of last dose or the last activity date of smart bottle data, whichever is earlier.

The percentage adherence over 12 weeks for each eligible subject is defined as:

$$100 \times (\text{total number of smart bottle openings over the first 12 weeks excluding the physician-directed interruption periods of the first 12 weeks}) / [2 \times (12 \text{ weeks (ie, 84 days)} - \text{the number of physician-directed interruption days of the first 12 weeks})]$$

Note: (1) the physician-directed interruption is defined as the reported interruptions due to reasons not being “Non-compliance”; (2) if there are more than 2 smart bottle openings at any day, they will be counted as 2 in calculation of the adherence endpoints.

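### Interruption days leave the adherence score only if reported, and site physicians see the bottle record in Arm A only, so the same gap may be excused more often in Arm A than in Arm B

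*Protocol*

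**What the plan says.** **Scoring.** In SAP 8.3.2 the 12-week numerator is the "total number of smart bottle openings over the first 12 weeks excluding the physician-directed interruption periods of the first 12 weeks". The denominator is twice the difference between 84 days and "the number of physician-directed interruption days of the first 12 weeks". The score over the whole treatment duration has the same structure. A note to both formulas states that "the physician-directed interruption is defined as the reported interruptions due to reasons not being" non-compliance. So any reported interruption with another reason is removed. A gap that nobody reports stays in as missed doses.

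**Who sees the bottle record.** Protocol Table 8-1 gives site staff and physicians access to compliance status in Arm A. For Arm B the entry is "Real-time dosing data transfer to CRO/Vertex only". The text under the table adds: "Study physicians will access dosing adherence data and review them with subjects in Study Arm A at scheduled study visits". Protocol 11.3.1 repeats the restriction ("Only subjects in Study Arm A will review data with study physicians at the study visits listed in" Table 3-2), as does footnote g of that table: "Subjects in Study Arm A will review data with physicians at study visits".

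**Where interruption data come from.** Protocol 12.3.2.4, on the complementary compliance analysis, says: "Information on number of pills and drug interruption will be collected from dispensing pharmacy and subjects". It makes no distinction by arm.

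**Final analysis.** The SAP introduction says the study was terminated early and that the planned analyses are replaced by descriptive summaries. SAP 5.1 and 8.3.1 list mean adherence over any treatment duration, mean adherence over 12 weeks, and the proportions at or above 80% and 90% over 12 weeks.

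**The concern.** Feedback from the bottle is the intervention, and it may legitimately change how subjects take their tablets. It should not change how identical behaviour is scored. In Arm A, a physician and subject looking at a dated trace have a reason to discuss each gap, and a non-compliance reason is the only one that leaves the days in the denominator. In Arm B the site has no trace to start from. The first scheduled review is at Week 12 (target Day 85 in SAP Appendix B), just after the 84 days that the 12-week endpoints cover. An interruption first entered at that review would be a retrospective explanation of a gap already visible.

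If reporting differs in this way, part of any difference between the arms in the mean, or in the 80% and 90% proportions, reflects ascertainment and not adherence. With no formal test planned, readers will take those by-arm figures at face value.

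**Working it through.** **Inputs from the documents**
- 12-week score: 100 × openings outside excused days / [2 × (84 − excused days)], with at most 2 openings counted per day (SAP 8.3.2).
- Design: SD 8, 50 against 25 subjects, difference 5.6 points, 80% power, two-sided 0.05 (Protocol 12.1, SAP 6.1).

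**Assumptions**
- One 5-day gap with no openings per affected subject.
- A net 20% to 50% of Arm A subjects have one such gap excused that would not have been excused in Arm B. The documents give no frequency.
- For the 48-week figures, the SAP rule applied to 48 × 7 = 336 days.

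**1. The plan's own figure.** The standard error of the difference is 8 × √(1/50 + 1/25) = 1.96. A noncentral t calculation with 73 degrees of freedom gives 80.5% power for 5.6 points, which agrees with the stated 80%. The 5.6 points are a difference between arm means over 48 weeks.

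**2. What a report does to the score of a gap with no openings**
- Not reported: counted as missed.
- Reported as non-compliance: counted as missed.
- Reported with any other reason: excused.

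Bottle review that moves a gap from the first state to the third raises the score. From the first to the second changes nothing. From the third to the second, or shortening an excused period, lowers it.

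**3. One subject.** Let b be adherence on the other days, g the gap and L the window. Excused, the score is b. Not excused, it is b × (L − g)/L. The difference is b × g/L.
- b = 100%, g = 5, L = 84: 158/158 = 100% against 158/168 = 94.0%, a difference of 5/84 = 6.0 points.
- b = 100%, g = 5, L = 336: 662/662 = 100% against 662/672 = 98.5%, a difference of 5/336 = 1.5 points.
- b = 85%, g = 5, L = 84: 85.0% against 0.85 × 158/168 = 79.9%, which crosses the 80% cut.
- b = 95%, g = 5, L = 84: 95.0% against 0.95 × 158/168 = 89.3%, which crosses the 90% cut.

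Longer gaps scale in proportion. At b = 90%, a 7-day gap is worth 7.5 points over 84 days and 1.9 over 336. A 14-day gap is worth 15.0 and 3.75.

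**4. Arm A mean.** Shift = net share × difference per subject.
- 12 weeks: 0.20 × 5.95 = 1.2 points; 0.50 × 5.95 = 3.0 points.
- 48 weeks: 0.20 × 1.49 = 0.3 points; 0.50 × 1.49 = 0.7 points.

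**5. Scale against the planned test.** A false shift of 0.5 points, inside the 48-week range, would have raised the rejection rate of the two-sided t-test from 5% to 5.7%. That test is no longer to be performed. The move to 12-week endpoints makes each gap weigh 336/84 = 4 times as much in the score.

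**The case against.** Four stronger readings are tempting, and the documents do not carry them.

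- **That Arm B sites have only unprompted recall.** Both arms have drug counts at Weeks 12, 24, 36 and 48. A 5-day gap leaves 5 × 4 = 20 extra tablets. All subjects are asked about adverse events at each visit, and each event needs an action taken, including drug interrupted (Protocol 13.1.1.3, 13.1.1.6). Interruptions for adverse events beyond 72 hours, and those for liver tests, go to the medical monitor (Protocol 10.6, 11.5.3). These routes narrow the asymmetry. They do not close it: a drug count does not date a gap, and the other routes are confined to adverse events or liver tests.
- **That prompting can only add excused days.** A physician holding the trace can also correct a wrongly claimed interruption or shorten its dates, and an Arm B site cannot. SAP 8.3.2 foresees such conflicts, since it lists bottle openings during excused periods. The direction is likely, not certain.
- **That the problem is independent of how reasons are classified.** A stop that a physician really ordered will usually be known to the site in either arm. The asymmetry bites mainly because every reported reason except non-compliance is excused, so the two issues are linked.
- **That 6.0 points exceed the 5.6 points the trial was sized for.** The first is one subject's score over 84 days. The second is a difference in means over 48 weeks.

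There is also a limit on what can be checked. Parts of the assessment schedule and of Protocol section 11 are not in the public text, and the eCRF is not available. The visible text has no rule that interruptions be recorded before the bottle review, no arm-blind classification, and no adherence summary without the exclusion. Such a rule could exist elsewhere.

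**Conclusion.** The concern holds as a risk of unequal ascertainment. Two features of the plan combine: excusal depends on a report, and sites see the dated bottle record in Arm A only. A gap with no openings can therefore be more likely to be excused in Arm A, and the likely net effect favours the activated bottle.

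The assumed net share of 20% to 50% of Arm A subjects, with one 5-day gap each and full adherence otherwise, gives 1.2 to 3.0 points on the 12-week mean and 0.3 to 0.7 on a 48-week mean. Individual subjects near 80% or 90% can change category over 12 weeks. The documents do not show that this happened, or how often.

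Because the final analysis is descriptive, what is exposed is the by-arm means and proportions, not an error rate. The sample size calculation is unaffected.

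**What to change.** 1. **Protocol Table 3-2 and 11.3.1.** At each visit in both arms, record interruptions and their reasons with the same question before any Arm A bottle report is opened. Flag entries made or changed after that review. After the early termination this helps only visits still to take place.
2. **SAP 8.3.2.** Keep the planned definition as the main summary. Add a by-arm sensitivity summary with no interruption days subtracted from numerator or denominator. Optionally add a second that subtracts only interruptions documented independently of the bottle data. Tabulate subtracted days per subject by arm.

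Replacing the main rule with interruptions documented through adverse events only is not recommended. Adverse events are also entered at visits, so they are not necessarily independent of the bottle review, and genuine directed stops for other reasons would count as missed doses.

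The cost is one line in the visit instructions, a SAP sentence and one or two extra tables. The no-exclusion summary will understate adherence for subjects with genuine directed interruptions, but by the same rule in both arms.
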